**Preparation or Update Date:**

**01/14/2021**

## Protocol Revision Summary

Date	Summary of Changes
01/14/2021	Protocol preparation for study registration

## BACKGROUND

1. Angiotensin receptor blocker neprilysin inhibitor (ARNI) sacubitril/valsartan (Entresto (1))
  - a. Approved in July 7, 2015
  - b. Indication: HF with reduced ejection fraction
2. PARADIGM-HF trial; ARNI vs enalapril (2)
  - a. N=8442, follow-up 2.3 years
  - b. Composite of cardiovascular death and HF hospitalization: 21.8% vs 26.5%
  - c. Safety endpoints: hypotension (14.0% vs 9.2%), renal failure (3.3% vs 4.5%), hyperkalemia (16.1% vs 17.3%), angioedema (0.4% vs 0.2%)
3. 2017 ACC/AHA/HFSA guidelines for management of heart failure (3)
  - a. The clinical strategy of inhibition of the renin-angiotensin system with ACE inhibitors (Level of Evidence: A), OR ARBs (Level of Evidence: A), OR ARNI (Level of Evidence: B-R) in conjunction with evidence-based beta blockers, and aldosterone antagonists in selected patients, is recommended for patients with chronic HFrEF to reduce morbidity and mortality.
  - b. The use of ACE inhibitors is beneficial for patients with prior or current symptoms of chronic HFrEF to reduce morbidity and mortality (Level of Evidence: A). Although the use of an ARNI in lieu of an ACE inhibitor for HFrEF has been found to be superior, for those patients for whom ARNI is not appropriate, continued use of an ACE inhibitor for all classes of HFrEF remains strongly advised.
  - c. The use of ARBs to reduce morbidity and mortality is recommended in patients with prior or current symptoms of chronic HFrEF who are intolerant to ACE inhibitors because of cough or angioedema (Level of Evidence: A). Head-to-head comparisons of an ARB versus ARNI for HF do not exist. For those patients for whom an ACE inhibitor or ARNI is inappropriate, use of an ARB remains advised.
  - d. In patients with chronic symptomatic HFrEF NYHA class II or III who tolerate an ACE inhibitor or ARB, replacement by an ARNI is recommended to further reduce morbidity and mortality (Level of Evidence: B).

- e. ARNI should not be administered concomitantly with ACE inhibitors or within 36 hours of the last dose of an ACE inhibitor (Level of Evidence: B). Oral neprilysin inhibitors, used in combination with ACE inhibitors can lead to angioedema and concomitant use is contraindicated and should be avoided.
- f. ARNI should not be administered to patients with a history of angioedema (Level of Evidence: C).

4. 2021 ACC/AHA/HFSA focused update (4)

[figure not shown]
- a. For patients with newly diagnosed Stage C HFrEF, a beta-blocker and an ACEI/ARB/ARNI should be started in any order. Each agent should be up-titrated to maximally tolerated or target dose. Initiation of a beta-blocker is better tolerated when patients are dry and an ACEI/ARB/ARNI when patients are wet.

## **STUDY OVERVIEW AND DESIGN**

- 1. Study aims: To emulate a prospective surveillance of the effectiveness and safety of ARNI vs a comparator (ARB) in older adults with HFrEF and different frailty status.
- 2. Data source(s): Data from 2014 up to 2020 will be used.
  - a. Medicare Database
  - b. Optum Database
  - c. MarketScan Research Database
- 3. Sequential cohort monitoring design (see Figure 1): The monitoring analysis will include 1) retrospective analysis of available data (2015-2017) at the time of first analysis (January 2021) and 2) prospective analysis of new data (2018-2020) as they become available to the researchers. Within each database, we will emulate biannual updating of data by creating a propensity score (PS)-matched cohort of new users every 6-month interval, beginning on the first marketing of ARNI (July 7, 2015-December 31, 2015, and 6-month intervals afterwards). Each sequential cohort will be followed for development of the outcomes of

interest. Outcome analysis will be performed at a pre-specified 6-month interval (prospective analysis). The surveillance will be performed by frailty status (frail vs non-frail) at the time of drug initiation. The results from each database will be pooled using fixed-effects meta-analysis (assuming low heterogeneity across the databases).

**Figure 1. Schematic of sequential monitoring design**

[figure not shown]

## STUDY POPULATION

1. Study population (see Figure 2) is created for each calendar interval.
2. Initiation of ARNI or comparator (ARB)
  - a. ARB: any of azilsartan, candesartan, eprosartan, Irbesartan, losartan, Olmesartan, telmisartan, valsartan
  - b. Index date (day 0): prescription fill from July 7, 2015

3. Assessment of eligibility (eligibility assessment window: [-365, 0] days) – See Appendix for list of codes.
  - a. Continuous enrollment for medical and drug insurance (Part A, B, and D)
  - b. Diagnosis of HF (outpatient diagnosis x2 or inpatient x1)
  - c. Reduced EF (<45%) algorithm (5)
  - d. No prior use of ARNI or comparator (exposure wash-out window: [-365, -1] days)
  - e. No recent HF hospitalization, defined as HF diagnosis (Appendix) in the primary position in the inpatient dataset (outcome wash-out window: [-60, 0] days)
  - f. No recent nursing facility stay, defined as any of the following claims in [-60, 0] days
    - i. Place of service: 31 (skilled nursing facility), 32 (nursing facility), 33 (custodial care facility)
    - ii. CPT codes: 99301, 99302, 99303, 99311, 99312, 99313, 99315, 99316, 99379, 99380, G0066
  - g. Excluded if age <65 years or exposure to both drugs on day 0
  - h. Contraindication to either drug (exclusion assessment window: [-60, 0] days, unless specified otherwise)
    - i. Hypotension
    - ii. Chronic kidney disease stage IV or V or dialysis
    - iii. Acute kidney injury
    - iv. Hyperkalemia
    - v. Angioedema: [-beginning of data, 0] days
  - i. If a patient meets the above-mentioned eligibility criteria more than once, only the first record will be included.

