## 3. Covariates

- a. Sociodemographic information: age, sex, race, dual eligibility
- b. Diseases: Chronic Conditions Data Warehouse (CCW) chronic conditions (see Table 2), provided in the Medicare Beneficiary Summary File (first date of satisfying the claims-based algorithm for individual conditions is available; considered present if this date is earlier than the index date)
- c. Prescription drugs: ATC3 classes with prevalence threshold  $>1\%$  in a representative Medicare sample
- d. Gagne combined comorbidity score (6)
- e. Claims-based frailty index (7): Frailty status will be defined as non-frail if  $<0.20$  or frail if  $\geq 0.20$

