E1129	25040	Type 2 diabetes mellitus with other diabetic kidney complication	Diabetes with renal manifestations, type II or unspecified type, not stated as uncontrolled
E1165	25042	Type 2 diabetes mellitus with hyperglycemia	Diabetes with renal manifestations, type II or unspecified type, uncontrolled
E1321	25040	Other specified diabetes mellitus with diabetic nephropathy	Diabetes with renal manifestations, type II or unspecified type, not stated as uncontrolled
E1322	25040	Other specified diabetes mellitus with diabetic chronic kidney disease	Diabetes with renal manifestations, type II or unspecified type, not stated as uncontrolled
E1329	25040	Other specified diabetes mellitus with other diabetic kidney complication	Diabetes with renal manifestations, type II or unspecified type, not stated as uncontrolled
I120	40391	Hypertensive chronic kidney disease with stage 5 chronic kidney disease or end stage renal disease	Hypertensive chronic kidney disease, unspecified, with chronic kidney disease stage V or end stage renal disease
I129	40390	Hypertensive chronic kidney disease with stage 1 through stage 4 chronic kidney disease, or unspecified chronic kidney disease	Hypertensive chronic kidney disease, unspecified, with chronic kidney disease stage I through stage IV, or unspecified
I130	40491	Hypertensive heart and chronic kidney disease with heart failure and stage 1 through stage 4 chronic kidney disease, or unspecified chronic kidney disease	Hypertensive heart and chronic kidney disease, unspecified, with heart failure and with chronic kidney disease stage I through stage IV, or unspecified
I1310	40490	Hypertensive heart and chronic kidney disease without heart failure, with stage 1 through stage 4 chronic kidney disease, or unspecified chronic kidney disease	Hypertensive heart and chronic kidney disease, unspecified, without heart failure and with chronic kidney disease stage I through stage IV, or unspecified
I1311	40492	Hypertensive heart and chronic kidney disease without heart failure, with stage 5 chronic kidney disease, or end stage renal disease	Hypertensive heart and chronic kidney disease, unspecified, without heart failure and with chronic kidney disease stage V or end stage renal disease

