I132	40493	Hypertensive heart and chronic kidney disease with heart failure and with stage 5 chronic kidney disease, or end stage renal disease	Hypertensive heart and chronic kidney disease, unspecified, with heart failure and chronic kidney disease stage V or end stage renal disease
N181	5851	Chronic kidney disease, stage 1	Chronic kidney disease, Stage I
N182	5852	Chronic kidney disease, stage 2 (mild)	Chronic kidney disease, Stage II (mild)
N183	5853	Chronic kidney disease, stage 3 (moderate)	Chronic kidney disease, Stage III (moderate)
N184	5854	Chronic kidney disease, stage 4 (severe)	Chronic kidney disease, Stage IV (severe)
N189	5859	Chronic kidney disease, unspecified	Chronic kidney disease, unspecified
N250	5880	Renal osteodystrophy	Renal osteodystrophy
N251	5881	Nephrogenic diabetes insipidus	Nephrogenic diabetes insipidus
N2581	58881	Secondary hyperparathyroidism of renal origin	Secondary hyperparathyroidism (of renal origin)
N2589	58889	Other disorders resulting from impaired renal tubular function	Other specified disorders resulting from impaired renal function
N259	5889	Disorder resulting from impaired renal tubular function, unspecified	Unspecified disorder resulting from impaired renal function
End-Stage Renal Disease (ESRD) Dx			
ICD10	ICD9	ICD10 Description	ICD9 Description
I953	45821	Hypotension of hemodialysis	Hypotension of hemodialysis
N185	5855	Chronic kidney disease, stage 5	Chronic kidney disease, Stage V

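### The exclusion for stage IV/V kidney disease or dialysis searches only the last 60 days, although 365 days of claims are required, so an unknown share of such patients can enter

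*Protocol*

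**What the plan says.** Protocol, STUDY POPULATION, item 3 opens with an "eligibility assessment window: [-365, 0] days", and item 3a requires continuous medical and drug coverage. Item 3h then sets a shorter look-back for contraindications: "exclusion assessment window: [-60, 0] days, unless specified otherwise". Five conditions follow. Item 3h(ii) is "Chronic kidney disease stage IV or V or dialysis", with no window of its own, so the 60-day default applies. Only item 3h(v) departs from the default: "Angioedema: [-beginning of data, 0] days". No reason is given for using 60 days on the kidney item.

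Under MEASUREMENTS, Covariates, item 3b, a chronic condition is "considered present if this date is earlier than the index date". Table 2 lists chronic kidney disease once, without stage.

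The Appendix table headed with the item 3h(ii) label is wider than that label. It also holds stage 1, 2, 3 and unspecified codes, diabetic codes, and mixed-stage codes such as I130: "Hypertensive heart and chronic kidney disease with heart failure and stage 1 through stage 4 chronic kidney disease, or unspecified chronic kidney disease".

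**The concern.** Hypotension, acute kidney injury and hyperkalemia can resolve, so asking whether they were recent makes sense. Stage IV/V kidney disease is a standing condition. Its absence from 60 days of claims says little about whether the patient has it.

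The patients who slip through matter for the endpoints. Acute kidney injury and hyperkalemia are components of the primary safety composite, and death is part of the primary effectiveness composite. The propensity score sees kidney disease only as present or absent. Matching on that flag does not make severity equal between the arms. Using the same window in both arms does not settle the matter either, because the missed patients need not be equally common among ARNI and ARB initiators.

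**Working it through.** **Step 1: which look-back applies to what.**

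| Item | Nature | Look-back |
|---|---|---|
| 3e HF hospitalization, 3f nursing facility stay | worded as recent events | 60 days |
| 3h(i), (iii), (iv) hypotension, acute kidney injury, hyperkalemia | acute | 60 days |
| 3h(ii) stage IV/V or dialysis | chronic | 60 days (default) |
| 3h(v) angioedema | lasting relevance | all data |
| Covariates 3b, chronic kidney disease flag | chronic | any date before index |

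The kidney exclusion is the one lasting condition here with the short window.

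**Step 2: a concrete patient.** A stage IV code falls on day -61 and no listed kidney code follows. Item 3h does not exclude this patient. The same history can switch on the kidney disease flag in the propensity score, because that flag has no 60-day limit. A [-365, 0] window would exclude the patient.

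**Step 3: are the data there?** The earliest index date is July 7, 2015. Going back 365 days gives July 7, 2014, and the protocol uses data from 2014. Item 3a secures enrollment over that year.

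**Step 4: how large could the leak be?** The protocol gives no prevalence, coding frequency or count, so there is no figure to reproduce. What follows is illustration under assumed rates.

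Let r be the number of qualifying codes per year and w the window in days, counted inclusively (61 or 366).

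- Random timing: share missed = exp(-r·w/365). For r = 4, w = 61: exp(-0.668) = 51.2%.
- Regular spacing: share missed = max(0, 1 - r·w/365). For r = 4, w = 61: 1 - 0.668 = 33.2%.

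| Codes per year (assumed) | 60-day, random | 60-day, regular | 365-day, random | 365-day, regular |
|---|---|---|---|---|
| 2 | 71.6% | 66.6% | 13.5% | 0% |
| 4 | 51.2% | 33.2% | 1.8% | 0% |
| 6 | 36.7% | 0% | 0.2% | 0% |
| 12 | 13.5% | 0% | about 0% | 0% |
| 52 | about 0% | 0% | about 0% | 0% |

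**Step 5: share of the enrolled cohort.** With assumed prevalence p before exclusion and share missed m, the cohort share is p·m/(1 - p + p·m). For p = 5% and four randomly timed codes a year: 0.0256/0.9756 = 2.6%, against 0.1% with 365 days. At two codes a year it is 3.6% against 0.7%; at twelve, 0.7% against about 0%. Taking p from 3% to 10%, the 60-day figures run from 0.4% to 1.5% at twelve codes a year and from 2.2% to 7.4% at two.

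**Step 6: what r means.** Under the present list any listed kidney code triggers exclusion, including stage 3, unspecified and I130. For the 60-day columns, r is therefore the rate of any listed code. For a longer window restricted to stage-specific codes, r is the lower rate of those codes alone. The two sets of columns need not be read on the same row.

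**The case against.** The strongest reply has four parts.

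- **The list is broad.** A stage IV patient coded in the last 60 days as unspecified kidney disease, or under I130 (which is also on the heart failure list), is excluded anyway. This stands. It lowers the leak by an unknown amount.
- **Day 0 is not a random date.** It is the first fill of a new drug, so a recent contact and a recent code are plausible. The protocol does not state this, but it is a fair inference and also points to a smaller leak.
- **Dialysis is probably caught.** If dialysis is billed weekly or more often, almost none is missed in 60 days. This stands as an assumption, and it narrows the point mainly to stage IV/V without dialysis.
- **Sixty days is the protocol's convention, and the window is part of the rule.** It is true that no sentence contradicts another. The convention still does not fit a chronic condition, and the protocol departs from it for angioedema.

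Three stronger readings are tempting and are not supported.

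- **That many such patients enter.** The result depends entirely on the coding rate, and near zero is within the range.
- **That the hazard ratio is biased toward ARNI by a factor of 0.93 to 0.98.** That range comes from (1 + p_ARNI(RR-1))/(1 + p_ARB(RR-1)), with p the residual prevalence. It assumes initial prevalence of 8% to 12% in ARB and half that in ARNI, 37% to 61% missed, and a two- to threefold risk. The imbalance and its direction are assumed. The calculation also ignores matching, which includes diabetes, anemia, drug classes, the comorbidity score and the frailty index; these may carry some severity information.
- **That missed end-stage patients create false kidney injury events.** The Appendix acute kidney injury list does contain I120 and a dialysis encounter code. However, an event also needs a primary-position diagnosis at a hospitalization or ED visit, and dialysis patients are the group least likely to be missed. That is a separate question about the code list.

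**Conclusion.** The point holds in a limited form. Item 3h(ii) uses a 60-day search for a chronic condition when a year of claims is guaranteed. An unknown share of patients, mainly with stage IV/V disease not on dialysis and with no listed kidney code in that time, can therefore enter despite the exclusion the protocol names. The all-stage flag does not balance their severity, and they are at risk of events that form part of both primary composites.

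The documents fix neither the number of such patients nor the size or direction of bias after matching. The miss shares rest on assumed coding rates and independent timing. The text makes this a question of who is in the study population, with a possible consequence for confounding that it does not establish. Figure 2, which outlines the design, is not visible in the copy read and might show windows.

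**What to change.** In item 3h(ii), set the look-back to [-365, 0] days for codes specific to stage IV, stage V, end-stage disease and dialysis: for example N184, N185, N186, I120, I1311, I132, Z992 and the ESRD diagnosis and procedure lists, with their listed ICD-9 counterparts. Keep [-60, 0] for hypotension, acute kidney injury and hyperkalemia.

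Do not extend the window to stage 1-3, unspecified, mixed-stage (I129, I130, I1310) or diabetic codes. A longer search on those would remove more patients who do not have stage IV/V disease. Separately, reconcile that Appendix table with its label. Before extending the ESRD lists, check the entries whose ICD-10 description names neither kidney nor dialysis, such as the vascular-prosthesis complications and internal carotid occlusion. If the sponsor prefers 60 days, give the reason.

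This changes how an exclusion already in the protocol is ascertained. Who should be excluded on clinical grounds remains the sponsor's decision.

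The cost is a short edit to item 3h, a split of the code list, a re-run of cohort selection and matching on data already held, and a slightly smaller cohort. Reporting how many patients the longer window removes in each arm before matching would show how large the leak was.

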**Figure 2. Study design outline for comparative effectiveness and safety analysis**

## MEASUREMENTS

1. Exposure to ARNI or comparator
  - a. ARNI: sacubitril/valsartan (Entresto)
  - b. ARB (comparator): any of azilsartan, candesartan, eprosartan, Irbesartan, losartan, Olmesartan, telmisartan, valsartan
  - c. Note: prior ACEI use (commonly used for hypertension and HFrEF) is allowed. This choice will resemble a clinic situation that involves switching from ACEI to ARB or to ARNI.
  - d. Exposure risk window and gap between treatments allowed: 7 days (primary analysis) or 14 days (sensitivity analysis)

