## 2. Outcomes

- a. Effectiveness endpoint:
  - i. Primary: a composite of all-cause death or HF hospitalization
    - Note cardiovascular death was not used because National Death Index data were only available up to 2016. Instead, all-cause death was used.
    - HF hospitalization is defined as HF diagnosis primary position in the inpatient dataset
  - ii. Secondary: individual components separately
- b. Safety endpoint:
  - i. Primary: a composite of SAE, defined as any hospitalization or ED visit due to diagnosis codes in the primary position:
    - hypotension
    - acute kidney injury/acute kidney failure
    - hyperkalemia
    - angioedema
  - ii. Secondary: individual components

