## STATISTICAL ANALYSIS

### **Estimation of treatment effectiveness and safety within each database**

1. PS-matched cohorts: Within each surveillance cohort by frailty status (frail vs non-frail), we will use logistic regression that estimates the probability of receiving the drug of interest as a function of sociodemographic characteristics, diseases, prescription drugs, comorbidity index, and frailty index. Note that PS model will be fit separately by frailty status. We will perform a 1:1 ratio nearest-neighbor PS matching, with a caliper of 0.2 of the standard deviation of the logit PS (9). We will evaluate balance in covariates using standard mean difference (<0.1 is considered adequate balance) within each surveillance cohort.
2. Primary analysis for effectiveness and safety: For time-to-event analysis of the effectiveness and safety endpoints, we will use Cox proportional hazards regression to estimate the hazard ratios (HR) and 95% confidence intervals (CI) by frailty status (frail vs non-frail). The follow-up will begin on day 1 and end on the day of development of the effectiveness or safety endpoints or the earliest of the following censoring events: switching or discontinuation of the study drug, death not due to the outcome of interest, disenrollment, and end of data period (see Figure 2). Proportional hazards assumptions will be checked using Schoenfeld residuals.
3. Subgroup analyses for primary effectiveness and safety endpoints will be conducted by frailty status (frail vs non-frail):
  - a. age (65-74 years vs  $\geq 75$  years)
  - b. sex
  - c. race (black or non-black)
  - d. dual eligibility for Medicaid
  - e. major multimorbidity burden/pattern (informed by latent class analysis)
  - f. dementia (CCW definition)
  - g. HF hospitalization status ( $\geq 2$  or  $< 2$  in the past year)

4. Secondary analyses will be conducted by frailty status (frail vs non-frail):
  - a. secondary endpoints (individual components of primary effectiveness and safety composite endpoints)
5. Sensitivity analysis for primary effectiveness and safety endpoints will be conducted by frailty status (frail vs non-frail):
  - a. “intention-to-treat” analysis with a maximum follow-up time of 1 and 2 years from the index date
  - b. exposure risk window or grace period of 14 days

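### As-treated follow-up is closed 7 days after dispensed supply ends, with no exception for hospital or skilled-nursing days, so some still-treated patients are censored and their later deaths are missed

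*Protocol*

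**What the plan says.** Exposure is anchored on pharmacy claims. STUDY POPULATION, item 2.b: "Index date (day 0): prescription fill from July 7, 2015". MEASUREMENTS, item 1.d, fixes the tolerance: "Exposure risk window and gap between treatments allowed: 7 days (primary analysis) or 14 days (sensitivity analysis".

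STATISTICAL ANALYSIS, item 2, lists the events that end primary follow-up by censoring: "switching or discontinuation of the study drug, death not due to the outcome of interest, disenrollment, and end of data period". The list makes no exception for days spent in hospital or in a facility.

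Facility stays appear only as an entry criterion, in STUDY POPULATION, item 3.f: "No recent nursing facility stay, defined as any of the following claims in [-60, 0] days". Item 3.e does the same for earlier admissions: "No recent HF hospitalization, defined as HF diagnosis (Appendix) in the primary position in the inpatient dataset".

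The effectiveness endpoint (MEASUREMENTS, Outcomes, item a) is "Primary: a composite of all-cause death or HF hospitalization". Its components are analysed separately as secondary endpoints.

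Two sensitivity analyses of the primary endpoints bear on the point (STATISTICAL ANALYSIS, item 5). One is an intention-to-treat "analysis with a maximum follow-up time of 1 and 2 years from the index date". The other uses an "exposure risk window or grace period of 14 days".

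**The concern.** While a patient is in hospital or skilled nursing, the facility may supply the drug, so an outpatient fill need not appear even though treatment continues. The rules as written would then read the lapse in fills as stopping the drug and close follow-up. The patient has not stopped; exposure has been mismeasured. Weighting for discontinuation would not restore the correct exposure time.

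What is at stake is the completeness of deaths in the as-treated analyses. A long stay is plausibly a marker of approaching death, so this censoring is plausibly informative. Long stays are also plausibly more common among frail patients. Every primary estimate is reported by frailty status, so the death component could be less complete in one stratum than in the other. If typical fill lengths differed between ARNI and ARB users, completeness could differ by arm as well. The Protocol gives no figure for any of these.

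**Working it through.** The Protocol states no event count, days' supply or length of stay, so it has no figure to reproduce. The calculation below is an illustration.

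**Inputs from the Protocol.** Allowed gap g = 7 days (primary) or 14 days (sensitivity).

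**Assumptions.** Days' supply S = 30 or 90. Remaining supply R at the start of the stay is uniform on (0, S). No fill is recorded during the stay, and a refill is recorded on the day of discharge. The patient stays on treatment throughout.

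**When censoring falls.** The gap starts when dispensed supply ends, so censoring falls on day R + g after entry to the stay. The range is g to S + g and the mean is S/2 + g.
- S = 30, g = 7: days 7 to 37, mean 15 + 7 = 22.
- S = 90, g = 7: days 7 to 97, mean 45 + 7 = 52.
- S = 30, g = 14: days 14 to 44, mean 15 + 14 = 29.
- S = 90, g = 14: days 14 to 104, mean 45 + 14 = 59.

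**How often.** A stay of L days causes false censoring if L > R + g. The probability is min(1, max(0, (L − g)/S)). For example, L = 20, g = 7, S = 30 gives 13/30 = 43%, and L = 30 gives 23/30 = 77%. On S = 90 the same stays give 13/90 = 14% and 23/90 = 26%.

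| Stay (days) | S = 30, g = 7 | S = 30, g = 14 | S = 90, g = 7 | S = 90, g = 14 |
|---|---|---|---|---|
| 10 | 10% | 0% | 3% | 0% |
| 20 | 43% | 20% | 14% | 7% |
| 30 | 77% | 53% | 26% | 18% |
| 45 | 100% | 100% | 42% | 34% |

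A stay of 7 days or less never triggers censoring by itself under the primary rule. If L is read as days from entry to a death in the facility, the same formula gives the chance that this death falls after censoring.

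**One patient.** A 30-day fill on day 0, a non-HF admission on day 20, then skilled nursing until death on day 50. Supply ends on day 30, and follow-up closes on day 30 + 7 = 37 (or 30 + 14 = 44 in the sensitivity analysis). The death is not counted under either rule. If the supply end date were extended by the 30 days of stay, it would move to day 60 and the death would count.

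**Which deaths are affected.** If the stay begins with an HF hospitalization, the primary composite has already recorded its event, so nothing further is lost there. For the composite, the problem is confined to other admissions and to direct entry to a facility. For death analysed alone, stays that begin with an HF admission are affected too.

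**The case against.** The strongest objection is that this is silence on how treatment episodes are built, which a protocol commonly leaves to the SAP. The SAP was not at hand, and neither was the content of Figure 2, to which the analysis section refers for follow-up. Items 3.f and 1.d also do different jobs and do not contradict each other. That carries weight: silence about bridging alone would not be a finding. But the Protocol itself fixes the gap and the censoring rule, and applying the two literally produces the error.

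Second, the intention-to-treat analysis does not depend on continued fills. It counts these deaths for the primary composite, in both strata, within 1 or 2 years. This stands and limits the concern. Two gaps remain. That analysis also mixes in true stopping and switching, so it cannot isolate this error. And item 5 is stated for primary endpoints, so death alone has no stated intention-to-treat version.

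Third, bridging has its own misclassification, because some patients will have had the drug stopped in the facility. This also stands, and it is why both versions should be reported.

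A reader might infer more than the text supports:
- *Patients count as discontinued 7 days after entering a facility.* No; the 7 days start when dispensed supply ends.
- *Later deaths are lost to the study.* No; they are lost to the as-treated analyses.
- *A given share of all deaths is missing, or the hazard ratio is biased in a known direction.* The Protocol gives no basis for either. Censoring removes person-time as well as events, and the rule is the same in both arms.

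**Conclusion.** The concern holds for the as-treated analyses. Applied as written, the fill-based exposure, the 7-day gap and censoring at discontinuation close follow-up on some patients who are still treated during a long stay. Under the stated assumptions the effect is large for stays of several weeks on a 30-day supply, and smaller but present on a 90-day supply. The 14-day analysis reduces it without removing it.

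The result rests mainly on one outside assumption, that treatment given during a stay does not appear as a fill. Days' supply, length of stay and the uniform remaining supply are also assumed. The percentages are shares of stays of a given length, not shares of all patients or all deaths. That the censoring is informative and more frequent in the frail stratum is plausible but not shown. This is a worthwhile, inexpensive improvement to the exposure definition; it does not show that the primary hazard ratio is wrong.

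**What to change.** In MEASUREMENTS, item 1.d, state that inpatient and skilled-nursing days after day 0 do not count toward the allowed gap, and that the supply end date is extended by the length of the stay. The stays can be identified from the inpatient data already used for item 3.e and the HF outcome, and from the codes already listed in item 3.f.

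Report the unbridged version as a sensitivity analysis. Tabulate censoring for discontinuation during or shortly after such stays, by arm and frailty stratum, so that its frequency and any imbalance can be seen.

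The cost is one programming rule on claims already held, plus one table. The downside is that some patients whose drug was stopped in the facility are counted as exposed during the stay; the unbridged analysis shows how much this matters.
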